6.D.2. Visit 1 (Baseline Visit): N= 160 subjects will be randomly assigned to receive either ZNS (80 subjects) or placebo (80 subjects). We will use blocked stratified randomization with treatment site (VA Connecticut versus Bedford) and the use of other psychotropic medications (e.g., antidepressants) as the stratification variables, with block sizes of 4 in each stratum to achieve treatment balance throughout the randomization process. Within 21 days after the screening visit, eligible subjects undergo a two-hour pre-treatment assessment (described below). At the baseline visit, subjects will complete a packet of questionnaires. Subjects will receive their first medication management session and first supply of study medication during a treatment session (visit 1) scheduled on the same day, following completion of the baseline assessments.

Subjects will begin study medication (i.e., ZNS or matching placebo) at an initial dosage of 100mg/day. All subjects will be asked to bring any remaining capsules and the study medication container to their next and all subsequent clinic visits, so that capsule counts can be used to measure compliance. The subject begins 6-week titration phase, during which the dosage will be titrated up as indicated above and in Table 1. Subjects will be paid a nominal but fair amount of money in compensation for all visits, including follow-up visits. Table 1 shows the titration schedule:

TABLE 1: Medication Titration Schedule

Week	Placebo	Zonisamide dose
1	One capsule daily	100mg QHS
2	Two capsules daily	200mg QHS
3	Two capsules daily	200mg QHS
4	Three capsules daily	300mg QHS
5	Three capsules daily	300mg QHS
6	Four capsules daily	400mg QHS
7	Four capsules daily	400mg QHS
8-9	Five capsules daily	500mg QHS (Target dose)
10-16	Five or Six capsules daily, 7 weeks duration	Continue 500mg daily or optional increase to 600mg QHS, 7 weeks duration
17-18	TAPER: Decrease capsules by one a day every 3 days, over a period of up to 15 days	TAPER: Decrease dose 100mg every 3 days, over a period of up to 15 days

Table 1 notes: 7 weeks of titration to the 500mg daily target dose. 9 weeks at the target dose with the option to increase to 600mg daily after two weeks at target if treatment response is suboptimal and there are no significant side effects (no current moderate to severe AE's with 500mg daily).

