We will use the percentage of subjects with no heavy drinking days (**PSNHDD**) as the primary outcome variable. This outcome is the FDA recommended endpoint for pivotal trials, and is described in Falk et al., (2010). The PSNHDD can be derived from each subject's TLFB data. An important initial consideration in considering effectiveness will be to identify baseline differences between groups that may have occurred despite randomization. **Successful outcomes during the treatment trial will be defined in terms of a statistically significant difference on the primary outcome measure: PSNHDD, compared during the 8 weeks of active treatment at the target dose, allowing for a 6 week grace period for the medication titration.** For all analyses, heavy drinking days will be defined as follows; for men > 5 drinks in a day and for women > 4 drinks in a day. Patients will be followed irrespective of whether they continue to receive medication treatment, so that analysis will include all data available for the 8-week treatment period. The analysis will be **intent-to-treat**, and dropouts will be considered as having relapsed to heavy drinking. We will use a logistic regression analysis with PSNHDD as a categorical dependent variable. Medication condition (placebo or ZNS) will be the main independent variable, and we will include the variables of early onset of alcoholism (EOA, binary), and the use of additional psychotropics (e.g., antidepressants, a binary variable) as covariates. The α will be set at .05 for the primary outcome variable. Between site differences will be explored.

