We will use a mixed models approach to examine **secondary outcome measures (Specific Aim 2)** for a statistically significant difference in; drinks per week, and heavy drinking days per week, the outcomes used in the pilot study. The model will include fixed effects for medication group, week, and the interaction between medication and week, also controlling for pre-treatment drinking behavior data, and using a random effect for intercept. We will incorporate a grace period corresponding to the time it takes to titrate the medication to target dose into the models, and we will focus the primary analysis on the 8 weeks of treatment at the target dose. Aggregate outcome measures such as the percentage of heavy drinking days, which can be examined using several different methods, will be considered. A statistically significant difference on any of the secondary measures of both heavy drinking and drinking, with clinically significant effect sizes, will be considered a relative success for the medication. Additional secondary outcome measures will include changes in GGT level, measures of alcohol urge or craving to use (AUQ), measures of depression and anxiety, measures of physical health and quality of life (Q-LES-Q, the and the RAND-36) and level of alcohol-related problems (as measured on the SIP). These can also be performed with the mixed models approach. Statistical models evaluating time to relapse, drinking trajectories, percentage of abstinent days, drinks per drinking day, and total abstinence rates will be considered. **We will use the Bonferroni correction for the secondary outcomes and additional comparisons to guard against chance findings.**

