All secondary outcome analyses will be by intention to treat, a conservative approach that is aimed at avoiding an overestimation of the treatment effect and will include all subjects that take any medication and provide drinking data for at least one week. The use of multilevel repeated measure statistical models may increase the study power and potential to detect a treatment effect. This type of repeated-measures analysis 1) provides missing-data imputation procedures that are both conservative and logical; 2) allows for the measurement of the exact time that a given patient is measured at baseline and follow-up points, which need not be the same among patients; 3) plots and analyzes linear and non-linear time-course functions both overall and for subgroups of patients based on each patient's best estimate linear and non-linear regression line plots. We will use all available data on individuals and thus dropouts provide data until the point of dropout. The best-fitting variance-covariance structure between the repeated measures will be selected based on Schwartz-Bayesian Information Criterion (BIC). We will compare dropout patterns between groups and if there are concerns of informative dropout and/or informative intermittent missing data, we will use pattern mixture models (Hedeker and Gibbons, 1997) to perform sensitivity analyses to our main analyses. Adherence to the medication will be evaluated and factored into the analysis. We will evaluate and compare both medication conditions (placebo, ZNS) for percentage of prescribed pills taken. We do not expect a difference, but if one is found, we can then perform additional analysis on the main outcome variables to estimate treatment effects adjusted for percent pills taken. The number of MM sessions attended will be recorded and analyzed similar to the medication adherence.

The three-month follow up data will be gathered using a retrospective TLFB at the follow-up time point, and will be analyzed using logistic regression for PSNHDD, and either linear mixed models or Hierarchical Linear Modeling (HLM) for other outcomes. We will examine that drinking data between the end of treatment and the three-month time point and use the same outcomes as the main analysis. We will be able to examine for persistent effects of ZNS on drinking behavior and related outcomes. These analyses will include pre-treatment and within-treatment drinking data as covariates to evaluate the post-treatment effects of ZNS.

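### The primary PSNHDD model omits pre-treatment drinking and site; the test is valid, but pre-specifying both gives a modest gain at no material cost

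*Combined protocol and SAP*

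**What the plan says.** Section 6.I.2 makes PSNHDD the primary outcome, tested by logistic regression at α = .05. Medication is the main independent variable. On covariates: "we will include the variables of early onset of alcoholism (EOA, binary), and the use of additional psychotropics". On site: "Between site differences will be explored". On imbalance: "An important initial consideration in considering effectiveness will be to identify baseline differences between groups that may have occurred despite randomization". No consequence of finding a difference is given.

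Elsewhere the plan treats both omitted variables as important:

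- **Site.** Section 6.D.2 reads: "We will use blocked stratified randomization with treatment site (VA Connecticut versus Bedford) and the use of other psychotropic medications", in blocks of 4. So one stratification factor is in the primary model and the other is not.
- **Pre-treatment drinking.** Section 6.C needs a 90-day pre-treatment timeline follow-back (TLFB) for eligibility. The secondary mixed models in 6.I.2 concentrate on the same 8 weeks at target dose and are described as "also controlling for pre-treatment drinking behavior data".
- **Three-month follow-up.** Here the data "will be analyzed using logistic regression for PSNHDD", and the section adds: "These analyses will include pre-treatment and within-treatment drinking data as covariates to evaluate the post-treatment effects of ZNS".

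Specific Aim 1 in Section 3 names drinks per week as the primary outcome. If that governs, the mixed model already has pre-treatment drinking, and the gap is only the strata: it names neither site nor psychotropic use.

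**The concern.** Baseline drinking is a natural candidate predictor of whether a subject has any heavy drinking day on treatment, and randomisation is not stratified on it. Leaving it out has two effects. First, some power is lost if it is prognostic. Second, a chance difference between arms moves the primary estimate, in either direction.

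Because the plan says baseline differences will be looked for but not what follows, a gap seen in the data leaves room for choosing covariates afterwards. A win with zonisamide (ZNS) as the lighter-drinking arm, or a near miss with ZNS as the heavier-drinking arm, would be hard to interpret.

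The secondary mixed models are the closest comparison, since they cover the same period. The follow-up analysis has a different aim (effects after treatment), so it is weaker support.

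**Working it through.** **Inputs.** Section 6.I.6 gives pilot counts of 12 (ZNS) and 7 (placebo) without relapse. Section 3 gives a pilot N of 40. The split by arm is not stated; 20 per arm is assumed, so 60% v 35%. Trial size is 80 per arm, with 64 per arm as the shortfall case. A two-sided test is assumed.

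**Reproducing the stated power.** With pooled rate .475,

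z = [.25√n − 1.96√(2 × .475 × .525)] / √(.60 × .40 + .35 × .65)

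- n = 80: (2.236 − 1.384)/.684 = 1.246, power **.894**. The stated figure of over 89% reproduces.
- n = 64: (2.000 − 1.384)/.684 = .901, power .816. The stated 76% or so reproduces only with a continuity correction (.764) or Fisher's exact test (.756). The N=128 results below use a Wald test, so they start from the higher level.

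**Simulated power.** Settings:

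- Permuted blocks of 4 within site × psychotropic strata; binary factors at 50% prevalence; Wald test; 60,000 trials per row.
- Planned model: treatment + EOA + psychotropic use.
- Assumed effects outside the first row: log-OR −0.5 each for EOA and psychotropic use, 0.7 for site; correlation 0.4 between latent EOA and baseline drinking.
- Marginal rates held at 35% v 60%.

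| Baseline OR per SD | Planned | + site | + baseline | + both | N=128: planned → both |
|---|---|---|---|---|---|
| nothing prognostic | .892 | .893 | .892 | .893 | .814 → .816 |
| 0.67 | .907 | .912 | .915 | .920 | .834 → .852 |
| 0.61 | .908 | .913 | .919 | .923 | .834 → .858 |
| 0.37 | .910 | .914 | .946 | .948 | .841 → .897 |

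The first five columns are N=160. The gain is 0.1 to 3.8 points at N=160 and 0.2 to 5.6 at N=128. When site is the only prognostic factor, adding it gives .894 → .900 (site OR 2) or .903 → .923 (site OR 4).

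A second simulation with different assumed strengths (site OR 1.65; baseline OR 0.61, 0.45 and 0.30 per SD) gives .893 → .914, .899 → .931 and .903 → .948 at N=160.

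**Dropout.** Under 6.I.2, "dropouts will be considered as having relapsed to heavy drinking". If dropout is unrelated to drinking and the overall rates stay at 35% v 60% (40,000 trials, N=160):

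| Dropout | OR 0.61: planned → both | OR 0.37: planned → both |
|---|---|---|
| 20% | .901 → .911 | .904 → .925 |
| 35% | .893 → .899 | .895 → .905 |

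**Chance imbalance.** The SD of the arm difference is √(2/80) = .158 SD. A gap over .25 SD is 1.58 standard errors, so its probability is .114, or .057 in each direction. Power at N=160 given such a gap:

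| | OR 0.61: planned v both | OR 0.37: planned v both |
|---|---|---|
| ZNS heavier | .829 v .918 | .750 v .942 |
| ZNS lighter | .963 v .918 | .986 v .944 |

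The planned risk difference moves by 8.1, 9.8 or 16.7 points per SD of gap (OR 0.67, 0.61, 0.37), so a .25 SD gap shifts it by about 2.0, 2.4 or 4.2 points. The adjusted one moves by 0.2 to 0.4 points per SD, so by 0.1 or less.

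**Type I error** (47.5% in both arms, 40,000 trials). With both terms it is .050 to .053. Under the planned model it is .046 to .051, falling to .038 if site alone is prognostic with OR 4. Omitting site is therefore conservative, not anti-conservative.

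**Effect measure.** The mean log-OR rises from 1.11 to 1.21 (OR 3.0 to 3.4) at baseline OR 0.61, and from 1.13 to 1.38 (OR 3.1 to 4.0) at 0.37. The mean standardised risk difference stays at .250.

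**The case against.** The strongest reply is that nothing here is an error. Outcome, model, covariates and α are named in advance, and which further covariates to add can be called preference. Several specific points stand:

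- The top of the range needs a baseline OR of 0.37 per SD (about 7-fold odds between −1 and +1 SD, since 1/0.37² = 7.3) and no dropout. Section 6.I.6 contemplates dropout of up to 40%. With 20% to 35% unrelated dropout the gain is about 0.5 to 2 points. If heavier drinkers drop out more, it shrinks less: about 1.8 points at 20% dropout and OR 0.61.
- Site adds little: 0.1 to 0.9 points in the main scenarios.
- The imbalance figures are conditional on an event of about 6% probability in each direction. One direction favours the planned model, and the overall power figures already average over both. They show sensitivity to luck, not a further power gain.
- The risk of post hoc covariate choice is inferred from silence. Section 7's expectation of statistical control concerns co-occurring disorders, not drinking.
- Only 35% v 60% is examined in the main runs. A 19/21 or 21/19 pilot split would put the simple power at 97% or 73%. At 10% v 25% (about 28 successes) adding both terms still costs nothing (.730 v .730 with no prognostic value). At 5% v 15% (about 16 successes) some 1.5% to 2% of fits fail, with or without the extra terms.

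These points limit the size of the benefit. None gives a reason to leave out a covariate already collected and used in the plan's other drinking analyses, or a factor used to randomise.

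**Conclusion.** The concern holds as an improvement in efficiency and pre-specification, not as a fault in validity. If PSNHDD is primary, adding baseline drinking and site is worth about 0 to 4 points of power at N=160 and 0 to 6 at N=128, less with much unrelated dropout. It also makes the result nearly independent of which arm happens to drink more at baseline. Baseline drinking supplies nearly all the gain; the case for site is mainly that the analysis should match the randomisation.

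The sizes rest on assumed prognostic strengths, an assumed 20/20 pilot split and 50% prevalences. The direction does not depend on the exact values: with no prognostic value at all, nothing is lost. If drinks per week is primary, only the missing strata remain; that case was not simulated.

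**What to change.** Before unblinding, amend Section 6.I.2 to:

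1. Specify the primary logistic model as treatment, site, psychotropic stratum as recorded at randomisation, EOA, and baseline heavy drinking days per week as a continuous term.
2. Name the TLFB window for that term. The plan collects 90 days pre-treatment (6.C) and 7 days before screening (6.D.1). These do not conflict, and the 90-day window is already needed for eligibility.
3. State that baseline differences will be described but will not change the covariates of the primary model.
4. State whether the reported effect is the conditional odds ratio or a standardised risk difference, because the former will be larger than under the planned model.
5. Optionally, name a penalised-likelihood fallback in case successes are few.

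If drinks per week is confirmed as primary, add only site and the psychotropic stratum to the mixed model.

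The core change (items 1 to 4) costs two model terms and three or four sentences. It needs no new data, and there is no power loss if neither term is prognostic.

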Specific Aims 1- 5, Effectiveness of ZNS in the Treatment of Alcohol-Dependent Veterans: We propose to conduct a 16 week, randomized, double blind, placebo-controlled study of ZNS in **N=160** regularly heavy drinking veterans with AD in the context of a minimal ambulatory psychosocial treatment aimed at enhancing adherence to medication (Medical Management, MM), (68). We will recruit and enter **160** subjects with which the study will be adequately powered. *All subjects must be currently alcohol dependent. The target dosage for ZNS is 500mg/day, which will be titrated up over the first 7 weeks of treatment, with dosage increases based on tolerability. The titration schedule will start with 100mg daily, increased to 200mg/day after the first week,*

and then increased by 100mg/day every 2 weeks to the **target dose of 500mg/day**. Subjects will then begin 9 weeks at the target dose with the option to increase to 600mg daily after two weeks at target if treatment response is suboptimal and there are no significant side effects (no current moderate to severe AE's with 500mg daily). Dosing will remain flexible with respect to the time of day that the medication is administered, in order to maximize compliance and minimize the impact of adverse effects. The dosage will be held or reduced based on the appearance of moderate-to-severe adverse effects. **Following the seven week titration phase, subjects will begin the 9 week period of active treatment on the target dose, followed by up to 2 weeks of tapering and discontinuation of the medicine, and a return for follow-up at three months post-treatment. The dosing is also flexible in that it will allow subjects to continue on at less than the target dose based on tolerability, but subjects must be able to tolerate at least 200mg/day (two pills). Also, if subjects are not having moderate to severe side effects during the treatment phase, and have not yet reached 600mg/day, they may be increased by up to 100mg every 2 weeks if it is felt that they may benefit further from it. This will allow maximum flexibility and optimal dosing.**

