6.I.6. Sample Size And Power Estimate (Specific Aims 1-3):

For the primary outcome PSNHDD: Based on the trend in the pilot study favoring ZNS with 12 subjects in the ZNS group without relapse to heavy drinking, and only 7 in the placebo group, we estimated the power with the previously planned sample size. Based on these proportions, we should be well powered (>89%) to detect a difference in PSNHDD with 80 in each group. Since dropouts will be counted as relapsed to heavy drinking, we will still be powered at that level, regardless of the number of dropouts. Even in the event that we don't recruit as many subjects as expected (e.g., N=64 in each group, approximately) we estimate the estimated power will be about 76% to detect a difference between the medication and placebo.

For secondary outcomes: Based on the effect sizes from our pilot study of ZNS (showing a small effect size on heavy drinking and a moderate effect size on total drinking), we estimated that a study with **N=160** (subjects) would be well powered (>.98) to detect a significant difference on the secondary outcomes heavy drinking days per week, and total drinks per week. In our pilot study we ran a linear mixed models and found a decrease in drinking of 1.4 drinks per week for the controls versus 2.2 drinks per week for ZNS. The variance in the decrease in drinking (slope) was approximately 0.9. Assuming similar results, a Monte Carlo simulation in Mplus showed that with a sample of 160 subjects evenly split between groups and measured weekly over 12 weeks there is power of 0.98 to detect a significant difference in slopes between groups. Also, in our pilot study we found a decrease in heavy drinking days per week of 0.2 for the controls versus 0.3 for ZNS. The variance in the decrease in drinking (slope) was about 0.1. Assuming similar results, a Monte Carlo simulation in Mplus showed that with a sample of 160 subjects evenly split between groups and measured weekly over 12 weeks there is power of 0.99 to detect a significant difference in slopes between groups. **Even if dropouts reached 40%, we will be well powered (>.80) for detecting differences on secondary outcomes.**

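### The secondary mixed model does not name its test term, and its only stated power is for a 12-week slope difference although the analysis focuses on 8 post-titration weeks

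*Combined protocol and SAP*

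**What the plan says.** Section 6.I.2 describes the secondary model for drinks per week and heavy drinking days per week. It has "fixed effects for medication group, week, and the interaction between medication and week". Baseline drinking enters as a covariate, and the only random effect listed is the intercept. On timing it says "We will incorporate a grace period corresponding to the time it takes to titrate the medication to target dose into the models", and that "we will focus the primary analysis on the 8 weeks of treatment at the target dose". Success is worded generally: "A statistically significant difference on any of the secondary measures of both heavy drinking and drinking", with clinically significant effect sizes. No term is named as the test, and the coding of week is not given. A Bonferroni correction applies to the secondary outcomes, but the number of tests is not stated.

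Section 6.I.6 is the only place where the secondary effect takes a statistical form. For drinks per week it uses pilot slopes of 1.4 and 2.2 and a slope variance of about 0.9. It reports that with 160 patients "measured weekly over 12 weeks there is power of 0.98 to detect a significant difference in slopes between groups". Heavy drinking days get the same treatment, with power 0.99. Power is said to stay above 0.80 with 40% dropout.

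Table 1 (section 6.D.2) reaches 500 mg in week 8. For weeks 10-16 it reads "Continue 500mg daily or optional increase to 600mg QHS, 7 weeks duration". The overview in 6.A also allows flexible increases during treatment.

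**The concern.** Three parts of the plan do not fit together. The model allows several tests. The power section describes one of them, a slope difference. The analysis window starts after titration, when much of any divergence between the arms may already have happened.

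If the drug works by the time target dose is reached and the gain holds, the arms run parallel in the analysed weeks. The medication-by-week term is then zero, however large the benefit. If the medication coefficient is used instead, the interaction in the model makes it the difference at whatever point the week variable equals zero. An uncentred coding can place that point far outside the data.

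A choice that changes the result is therefore left open and could be settled after the data are seen. The outcomes matter: 6.I.2 counts a significant secondary difference as a relative success for the drug, and Specific Aim 1 names drinks per week as the primary outcome, although 6.I.2 treats it as secondary.

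**Working it through.** **Inputs from 6.I.6:** slope difference 2.2 - 1.4 = 0.8; slope variance 0.9; 80 per arm; 12 weekly measures; power 0.98.

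**Assumptions:** two-sided alpha 0.05 (the simulation's alpha is not stated), equally spaced weeks, and a test that allows for patient-to-patient slope variation.

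**Formulas:** variance of one patient's estimated slope = 0.9 + R/Sxx, where R is the residual variance and Sxx the sum of squared deviations of the week numbers (143 for 12 weeks, 60 for 9, 42 for 8). SE of the difference = sqrt(2 x variance / n per arm). Power = Phi(0.8/SE - z).

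**1. The plan's own figure.** With R = 0, power is 0.9996, which is a ceiling. To reach 0.98, SE must be 0.8/(1.960 + 2.054) = 0.1993. The slope variance is then 0.1993² x 40 = 1.589, and R = (1.589 - 0.9) x 143 = 98.5 (SD about 9.9 drinks per week). So 0.98 is attainable, but only with a residual variance that the plan does not report.

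The 0.99 for heavy drinking days cannot be reproduced from its stated inputs. With difference 0.1 and variance 0.1 the ceiling is 0.516. It becomes attainable only if 0.1 is an SD. That is a separate problem, so the rest uses drinks per week.

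**2. The same slope test in the analysed window, arms still diverging.** Over 8 weeks the variance is 0.9 + 98.5/42 = 3.246.

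| Weeks | n per arm | alpha | Power |
|---|---|---|---|
| 12 | 80 | 0.05 | 0.98 |
| 12 | 48 | 0.05 | 0.875 |
| 9 | 80 | 0.05 | 0.887 |
| 9 | 48 | 0.05 | 0.691 |
| 8 | 80 | 0.05 | 0.802 |
| 8 | 48 | 0.05 | 0.585 |
| 8 | 80 | 0.025 | 0.715 |

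The 48 is 60% of 80, with dropouts contributing nothing. Alpha 0.025 is Bonferroni for two outcomes only. Nine weeks is the length at target dose in Table 1, which differs from the 8 in 6.I.2.

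Because 0.98 is rounded, R is not pinned down. Power of 0.975 at 12 weeks gives R = 109.5, and 0.985 gives R = 85.9. The 8-week results then range over 0.77-0.84 (80 per arm), 0.55-0.63 (48 per arm) and 0.68-0.76 (alpha 0.025).

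**3. A stable effect.** In 20,000 simulated trials (80 per arm, 8 weeks, constant shift of 0.3 or 0.5 SD of one weekly value, within-patient correlation 0.4-0.8), the medication-by-week test rejected in 0.049-0.052. This is alpha, as it must be. The averaged difference in the same weeks rejected in about 0.54-0.78 for 0.3 SD and 0.93-0.996 for 0.5 SD.

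**4. The medication coefficient.** With total variance 1 and correlation 0.6, its variance is (0.6 + 0.4 x (1/8 + c²/42)) x 2/80, where c is the distance from the zero of the week variable to the middle of the window. For a 0.5 SD shift:
- week centred, c = 0: 0.01625, power 0.975
- week coded 1-8, c = 4.5: 0.02107, power 0.93
- week coded 9-16, c = 12.5: 0.05345, power 0.58

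The data and the model are the same in all three cases.

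**5. What the averaged contrast would need.** Take the plan's slope difference over 7 titration weeks as a stable gap: 0.8 x 7 = 5.6 drinks per week. With variance B + 98.5/8 and 80 per arm, power is 0.92, 0.68, 0.42 and 0.22 for a between-patient variance B, after baseline adjustment, of 100, 200, 400 and 900. The plan gives no value for B.

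**The case against.** The strongest reply is that 6.I.2 never calls the interaction the test. The model keeps a medication-group term, success is simply a difference on the measure, and a power simulation does not define the analysis. With week centred, the group term is exactly the averaged difference. This stands. A reader might infer that the plan commits itself to a slope test, but the documents do not say so; the power section only implies it.

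A reader might also infer that the analysed weeks are at constant dose, so that no divergence is possible. That is not supported either. Table 1 permits an increase to 600 mg, and 6.A says of patients below 600 mg without moderate to severe side effects that "they may be increased by up to 100mg every 2 weeks if it is felt that they may benefit further from it". Some continuing divergence cannot be excluded. Nor does 6.I.2 flatly exclude the titration weeks: it builds a grace period into the models and focuses on the later weeks.

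A stable effect could also show through other analyses. The logistic analysis of patients with no heavy drinking days uses no slope, and aggregate measures are to be considered. This limits the harm but does not settle what the secondary mixed model tests.

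Lastly, the 0.05 is true by construction, and the 48-per-arm figure is pessimistic because 6.I.2 uses data up to dropout. Both are fair. Treated the same way, however, the 12-week design gives 0.875, which agrees with the claimed 0.80 or more; the 8-week design does not.

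**Conclusion.** The point holds as a specification gap together with a power mismatch. The test term and the week coding are unnamed, and the only powered contrast is a slope difference over 12 weeks, which is not the window on which the analysis focuses.

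If the slope is the test, power against a stable effect is about 0.05. If the arms keep diverging, power for drinks per week is about 0.80 over 8 weeks, not 0.98. It is about 0.585 with 40% dropout, against the claimed value above 0.80, and about 0.715 at alpha 0.025. Over 9 weeks the first two figures are 0.887 and 0.691.

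The diverging-arms figures rest on the back-solved residual variance of about 100, a two-sided alpha and a test that allows for varying slopes. Section 6.I.2 lists only a random intercept.

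It would be tempting to conclude that an averaged contrast is already shown to be well powered. The documents do not support that: they give no between-patient variance and no expected level difference, and step 5 shows how widely the answer moves. The case for the averaged contrast is that it measures a difference in level and does not depend on how week is coded.

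**What to change.** In 6.I.2, name one test for each secondary drinking outcome: the medication difference averaged over the analysed target-dose weeks, adjusted for pre-treatment drinking. This is equivalent to the group effect with week centred. State how week is coded, and report medication-by-week as supportive.

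Reconcile the number of analysed weeks between 6.I.2 and Table 1. In 6.I.6, restate the secondary power for that contrast, that number of weeks, the Bonferroni alpha (with the number of tests given) and the assumed dropout. Show the residual and between-patient variances as a range, from the pilot data where possible.

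The cost is a few sentences of analysis-plan wording and one re-run of the power simulation. No change to data collection or visits is needed. The change should be made before unblinding.
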